VBM grey matter density (GMD) images, DTI FA and MD images, task-related contrast images, RS-fcMRI component maps, and ASL CBF images will be compared between those receiving the combined intervention, a single intervention, and control cross-sectionally and longitudinally on voxel-wise and ROI levels. Cross-sectional voxel-wise analyses will compare the scans between groups at BL, PT, and FU. Longitudinal voxel-wise analysis will model time-by-group interactions using a two-way Analysis of Covariance (ANCOVA) model. All voxel-wise analyses will be performed in SPM8 (or SPM12). For regional analysis, we will extract a mean value for ROIs from the final stage preprocessed scans. Specifically, cross-sectional and longitudinal change in regional brain atrophy (i.e., MTL, frontal lobe), WM integrity (i.e., FA, MD from MTL WM tracts), task-related fMRI activation (i.e., activation from task-specific regions), resting-state connectivity (e.g., DMN connectivity from medial parietal lobe and MTL, etc.), and cerebral perfusion (i.e., whole brain, frontal lobe, etc.) will be compared between groups using values extracted from hypothesized target ROIs (see Analytic Plan).

Cost. We will track all personnel, equipment, technology, and support costs associated with delivering the interventions thus allowing an estimation of intervention costs on a per subject basis.

Power and Sample Size. The primary analysis of the study focuses on the evaluation of the effectiveness of the interventions on the cognitive outcome, ECC. We therefore determined the sample size to ensure adequate power for this analysis. In these prior studies, speed of processing training was found to have an effect size (ES) of 1.4 standard deviation (SD) at immediate post-training (PT) and 1.2 SD at one year PT on processing speed outcomes.(22) MIND diet is a brain health optimized hybrid of the Mediterranean-DASH diets, and the latter were found to have an effect size of 0.44 to 0.56 SD on executive function and speed of processing(136). There are no published trials of speed of processing training combined with MIND diet but we expect a large effect size of the combined intervention. With an overall alpha level of 0.05 for six Bonferroni-

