adjusted two-sided comparisons, a conservative estimate of the correlation of 0.7 between baseline and followup based on prior studies, and 15% attrition rate (in our recent GRACE trial of 951 older adults—62% had < 12yrs of education—91% completed the 6-month follow-up assessment)(73), the sample size of up to 50 participants per treatment arm will yield 80% power to detect an effect size of >0.5 SD based on the constrained longitudinal data analysis (cLDA).(137) The cLDA (138) has been shown to produce greater efficiency and handle missing data more flexibly with valid inference when data are missing at random.(137, 139). Cognitive aging studies support an effect size of over one-half standard deviation as clinically meaningful.(140-142)

Exploratory Aims and Power: Outcomes include inflammation, metabolic function, oxidative stress, and hippocampal structure and function (via MRI). For non-imaging outcomes, we will have a full sample and adequate power to detect effect sizes of 0.6. Imaging creates anxiety and discomfort for some, however. Thus, in addition to using information and communication strategies shown to reduce imaging anxiety(143) we will complete imaging on the minimum necessary. From the literature, we anticipate large effect sizes on the brain outcomes of hippocampal structure and function. Cognitive training has resulted in changes in brain structure with approximate effect size of 0.56 in left hippocampus volume following spatial navigation training among healthy younger and older men(144) and an approximate effect size of 0.47 in gray matter density (GMD) after the completion of a multidomain computerized cognitive training among healthy older adults.(20) In addition, our preliminary results showed an effect size of 0.5 in annual percent change in hippocampal volume and 0.8 in annual percent change in hippocampal GMD among older adults without MCI who are frequently engaged in reading and puzzle-solving compared to those who are not. Food interventions alone have had an effect size of 0.7 on hippocampal volume.(9, 56) Other studies support effect sizes of 0.64 to above 1.00 on functional connectivity.(145, 146) A one-half subsample of each arm (n=22 per arm) with an alpha level of 0.05 and a correlation of 0.7 between baseline and post-training provides 80% power to detect an effect size of 0.7 or larger for the brain imaging outcome.

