The *primary analysis* of the intervention effect on ECC will be performed using the constrained longitudinal data analysis (cLDA) proposed by Liang and Zeger.(138) Repeatedly measured ECC outcome at BL, PT, and FU will be modeled as dependent variables with the baseline mean responses constrained to be the same across intervention arms due to randomization. This model is flexible in handling missing data and has been shown to provide greater power than other models when testing intervention effects and yields valid results when data are missing at random. The clustering effect of repeated measures within a subject will be accommodated using a random subject effect. Time of measurement (BL, PT, FU) and its interaction with intervention arm will be included in the model. The time of measurement is considered as a categorical variable to allow non-linear time effect. Intervention effects are captured by the significant interaction effect. Comparison of outcome measures across intervention arms at PT and FU will be estimated based on the

model using appropriate contrasts. In order to assess whether the intervention effect is affected by physical activity change, weight change, or other factor, we will examine change patterns across intervention arms. If the change pattern differs across intervention arms, that factor will be controlled by including its main effect and interaction with the intervention arm in the primary analysis for intervention effect on memory.

Exploratory Analyses. Feasibility hypotheses are 80% or greater intervention adherence and acceptability, and no serious adverse events. These will be estimated using the 95% confidence intervals. To compare safety, we will estimate the difference in rates of adverse events across the intervention arms using 95% confidence intervals. Hypotheses of improved self-reported outcomes including depression, cognition and engagement, quality of life, and IADL will be examined using the cLDA methods described immediately above.

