Mechanism Analyses. Mechanistic hypotheses are that, relative to control, intervention arm participants will have greater hippocampal volume, enhanced DMN and CEN connectivity at PT, better metabolic function, higher levels of neurotrophic growth factors, and lower levels of inflammation and oxidative stress. Hypotheses will be analyzed using cLDA. With regard to MRI, scan analysis described immediately above will be performed on targeted pre-specified ROIs and followed by spatially unbiased whole brain voxel-based analyses. Supplemental analyses will compare across scan modalities to address the relative incremental contribution of each modality (e.g. hippocampal volume) to capturing the overall neuroimaging outcome.

Moderator and Mediator Analyses. Analyses will be performed to determine the role of adherence, years of education, age, baseline cognitive scores, comorbidity, and *APOE* ε 4 carrier status (an indicator of elevated ADRD risk) in moderating intervention outcomes using cLDA. We hypothesize in particular that participants with greater adherence, more education, and lower comorbidity will experience larger ECC score gains. A three-way interaction between potential moderators, intervention arm, and time of measurement will be included in the model and a significant three-way interaction indicates the moderating effect. To evaluate hypothesized mediators of the speed training and MIND foods (e.g., inflammation, growth factors, oxidative stress, hippocampal volume), we will use the approach proposed by Krull and Mackinnon (2011) (147) that allows the testing of mediating effects in clustered data. Using the change in ECC outcome from baseline as the dependent variable, a series of three mixed effects models, as outlined by Krull and Mackinnon, will be fit and regression coefficients from these models will be used to estimate the direct and indirect treatment effects.

The cLDA provides valid inference when data are missing due to random dropouts. Sensitivity analyses will be performed to examine to what extent the results are affected when dropouts are not missing at random. Analyses based on complete cases, mean imputation, and worst case imputation will be performed. In addition, a pattern mixture model will be used to allow different intervention effects for subjects with different missing data patterns. Results based on these models will be compared to results from cLDA.

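### Two of the four analyses planned for non-random dropout do not explore it in a controlled way, and nothing graded is specified between MAR and the worst-case bound

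*Combined protocol and SAP*

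**What the plan says.** The closing paragraph of Moderator and Mediator Analyses (Analytic Plan) sets the aim: "Sensitivity analyses will be performed to examine to what extent the results are affected when dropouts are not missing at random". It then lists the methods: "Analyses based on complete cases, mean imputation, and worst case imputation will be performed". The paragraph names one further method: "a pattern mixture model will be used to allow different intervention effects for subjects with different missing data patterns". On use, it says: "Results based on these models will be compared to results from cLDA".

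The primary analysis is a constrained longitudinal model (cLDA) of the executive cognitive composite (ECC) at baseline, post-training and 6 months. The plan says that this model "yields valid results when data are missing at random".

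The plan does not say which mean is imputed (arm, pooled, visit or subject). It mentions no variance correction or multiple imputation, and it gives no identifying restriction or shift parameter for the pattern-mixture model.

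**The concern.** A sensitivity analysis for MNAR has to relax the MAR assumption, preferably by an amount that can be varied and judged. Complete-case analysis and single mean imputation have no such parameter. Complete-case analysis is valid if loss is completely random or explained by covariates in the model. It also discards the post-training scores of participants lost before 6 months, which cLDA uses. Mean imputation supposes that dropouts sit at the observed mean, and then analyses those values as if they had been measured.

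What is at stake is how the comparison with cLDA is read. Agreement between cLDA and these two methods says little about MNAR, because all three rest on the same observed scores. Disagreement may be an artefact of the imputation. Study Considerations names retention as a feasibility challenge and links the efficacy result to a later prevention trial, so the question deserves an informative answer.

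**Working it through.** **Inputs.** All are from Power and Sample Size.
- Up to 50 per arm, and an effect of 0.5 SD.
- "a conservative estimate of the correlation of 0.7 between baseline and followup based on prior studies".
- Six Bonferroni-adjusted two-sided tests at 0.05 overall, so 0.05/6 = 0.0083 each (critical value 2.638).
- Loss m = 15%. As a second value, m = 9%, because 91% completed the 6-month visit in the team's earlier trial.

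**The plan's own figure.** The missing-data paragraph gives none. The nearest is the power statement, used here only to check the set-up. With residual SD √(1 − 0.7²) = 0.714 and 50 analysed per arm, power at 0.5 SD is 80.6%. With 50 × 0.85 = 42.5 per arm it is 72.2%, and the detectable effect is 0.539 SD, which still fits the plan's wording of above 0.5. That is a separate matter from this point.

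**Arm-mean imputation.** The imputed values add no spread but are counted in the sample size. For an arm mean, the naive variance is about (1 − m)s²/n, while the true variance is s²/[n(1 − m)]. The SE ratio is therefore about 1 − m, and the actual two-sided error is 2[1 − Φ(z(1 − m))].

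| Loss | SE ratio | Error at nominal 5% | Error at nominal 0.83% |
|---|---|---|---|
| 15% | 0.85 | 2[1 − Φ(1.96 × 0.85)] = 9.6% | 2[1 − Φ(2.638 × 0.85)] = 2.5% |
| 9% | 0.91 | 2[1 − Φ(1.96 × 0.91)] = 7.4% | 2[1 − Φ(2.638 × 0.91)] = 1.6% |

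The formula is for unadjusted means. It was checked by simulating 6,000 trials per scenario with 50 per arm, one post-baseline visit, correlation 0.7, baseline adjustment and 15% loss completely at random. Under no effect, the model SE was 0.141 against a true SE of 0.166 (ratio 0.85). Error was 9.0% at 5% and 2.3% at 0.83%.

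**Pooled-mean imputation.** Dropouts in both arms receive the same value, so with equal loss the difference becomes (1 − m) × 0.50. That is 0.85 × 0.50 = 0.425 at 15% and 0.91 × 0.50 = 0.455 at 9%. Simulation at 15% gave 0.423, with an SE of about the right size (ratio 1.01).

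**Complete case.** At one post-baseline visit, with a true effect of 0.50, the simulated estimate was 0.500 under completely random loss and 0.504 when loss depended on baseline. There is no bias in either case. The assumption becomes stronger than that of cLDA when loss at 6 months depends on the observed post-training score. This simulation has no second visit and does not size that case.

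**An assumed MNAR mechanism.** Suppose low post-training scorers drop out in the treated arm only (true effect 0.50, about 15% missing). The estimates were complete case 0.594, pooled mean 0.573 and arm mean 0.676. All are too high. In a separate three-visit simulation of 1,500 trials with loss of this kind, cLDA gave 0.60, complete case 0.62 and pooled mean 0.60: close agreement, all about 0.1 SD too high. The size of the bias depends on the assumed mechanism. In the one-visit simulation, worst-case imputation (lowest observed value to treated dropouts, highest to control dropouts) gave −0.18, so it does stress the result.

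**What a graded analysis would show.** If missing values in one arm are lowered by δ SD, the estimate moves by m × δ. Take an observed effect of 0.5 and hold the SE at √(2 × 0.51/42.5) = 0.155. Bonferroni significance is lost when 0.5 − 0.15δ < 2.638 × 0.155 = 0.409, so at δ of about 0.6 SD. The effect reaches zero at 0.5/0.15 = 3.3 SD. A reader can judge whether a 0.6 SD deficit in dropouts is plausible.

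**The case against.** The strongest reply is that the paragraph already contains MNAR methods. Worst-case imputation and the pattern-mixture model are both listed, and both are compared with cLDA. This stands. A reader might infer that the plan has no MNAR analysis; the documents do not support that.

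It can also be said that the inflated error rates belong to a supporting analysis that decides nothing. This stands too. A reader might infer that the trial's own type I error is inflated, but the primary cLDA estimate, its SE and its alpha are untouched. The plan also states no rule for declaring robustness, so false reassurance is a risk of interpretation and not a planned step.

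Third, pooled-mean imputation does impose one fixed departure from MAR, in the conservative direction under equal loss. That is fair, but the departure is arbitrary and cannot be varied.

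Fourth, it would be too strong to say that complete-case analysis always needs more than cLDA or is always more biased. With loss depending only on baseline it was unbiased.

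Finally, the arm-mean and pooled-mean figures are alternatives. Only one can apply, and which one is unknown until the plan names the mean.

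What remains is that two of the four methods do not serve the stated purpose in a controlled way. Of the other two, worst case is a single extreme, and the pattern-mixture model is not specified far enough to be run. Participants who never attend at 6 months supply no data on their 6-month effect, so an identifying restriction is needed.

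**Conclusion.** The point holds as a weakness of the sensitivity analyses, not of the primary analysis. Complete-case analysis and single mean imputation do not explore MNAR in a controlled way, and no graded analysis is specified between MAR and the extreme bound.

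Mean imputation also brings its own fault. An arm mean understates the SE (ratio about 0.85 at 15% loss, 0.91 at 9%; error about 9% and 7% at a nominal 5%). A pooled mean shrinks 0.50 SD to about 0.42 or 0.455. These sizes rest on equal loss across arms, completely random loss, and the plan's sample size and correlation; they are driven mainly by the missing fraction. Subject-mean and baseline-mean imputation were not sized.

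**What to change.** Replace mean imputation with delta-adjusted multiple imputation of the ECC, increasing the shift until the conclusion changes, and report that tipping point.

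Apply the shift contrast by contrast. The six comparisons are read here as all pairs of the four arms, three of which are active against active. A common shift in every active arm would cancel there when loss is equal: 0.15δ − 0.15δ = 0. That would leave no tipping point for MINDSpeed against either single intervention, which the primary hypotheses in Specific Aims include. Shift the arm hypothesised to be better, or use a two-way grid of shifts in both arms. The grid suits MIND food against Speed training, for which no direction is hypothesised.

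Keep worst case as a bound. Keep complete case only as a descriptive check, not labelled as an MNAR analysis. State the identifying restriction of the pattern-mixture model.

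The cost is a few sentences of analysis-plan text and a small amount of extra analysis in standard software. No new data and no change to trial conduct are needed.
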